8.7 Premature termination of the study

In case the study is ended prematurely, the investigator will notify the accredited IRB or METC within 15 days, including the reasons for the premature termination. Within one year after the end of the study, the investigator/sponsor will submit a final study report with the results of the study, including any publications or abstracts of the study, to the accredited METC.

9. SAFETY REPORTING

9.1 Temporary halt for reasons of subject safety

In accordance to section 10, subsection 4, of the WMO, the sponsor will suspend the study if there is sufficient ground that continuation of the study will jeopardize subject health or safety. The sponsor will notify the accredited METC without undue delay of a temporary halt including the reason for such an action. The study will be suspended pending a further positive decision by the accredited METC. The investigator will take care that all subjects are kept informed.

9.2 AEs, SAEs and SUSARs

9.2.1 Adverse events (AEs)

Adverse events are defined as any undesirable experience occurring to a subject during the study, whether or not considered related to the trial procedure. All adverse events reported spontaneously by the subject or observed by the investigator or his staff will be recorded, only if judged to be substantial deviating from expected standard

clinical course. This includes severe adverse events that influence postoperative recovery or clinical outcome.

9.2.2 Serious adverse events (SAEs)

A serious adverse event is any untoward medical occurrence or effect that

- results in death;
- is life threatening (at the time of the event);
- requires hospitalization or prolongation of existing inpatients' hospitalization;
- results in persistent or significant disability or incapacity;
- is a congenital anomaly or birth defect; or
- any other important medical event that did not result in any of the outcomes listed above due to medical or surgical intervention but could have been based upon appropriate judgement by the investigator.

An elective hospital admission will not be considered as a serious adverse event.

The investigator will report all SAEs to the sponsor without undue delay after obtaining knowledge of the events. Subjects will be followed up for AEs and SAEs until the final study procedures or 7 days after discontinuation of the study. All reports will be digitally filed in the electronic clinical research form; Castor ((Castor EDC, CIWIT B.V., www.castoredc.com).

The sponsor will report the SAEs through the web portal *ToetsingOnline* to the accredited METC that approved the protocol, within 7 days of first knowledge for SAEs that result in death or are life threatening followed by a period of maximum of 8 days to complete the initial preliminary report.

All other SAEs will be reported within a period of maximum 15 days after the sponsor has first knowledge of the serious adverse events.

9.2.3 Suspected unexpected serious adverse reactions (SUSARs)

Not applicable as in this study there is no investigational medicinal product.

9.3 Annual safety report

Not applicable as in this study there is no investigational medicinal product.

9.4 Follow-up of adverse events

All AEs will be followed until they have abated, or until a stable situation has been reached.

Depending on the event, follow up may require additional tests or medical procedures as indicated, and/or referral to the general physician or a medical specialist.

SAEs need to be reported till end of study within the Netherlands, as defined in the protocol

9.5 Data Safety Monitoring Board (DSMB) / Safety Committee

In this strategy study, which compares two standard-of-care rocuronium dosage regimens, there are no additional risks for the patients. We therefore see no need for a DSMB in this low risk study.

10. STATISTICAL ANALYSIS

10.1 Primary study parameter

Data will be analyzed comparing the incidence of adverse events during laparoscopic surgery, following the Classic criteria using χ^2 test with $p < 0.05$ considered significant. Data analysis will be performed using R Studio, Boston, MA, USA.

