Rationale: Muscle relaxants are routinely applied during anesthesia to facilitate endotracheal intubation and to improve surgical working conditions. Several investigations have shown that a deep neuromuscular block (NMB) improves the surgical working conditions over a standard NMB and effectively precludes sudden deterioration of the surgical field. However, whether the improvement of surgical working conditions translates into less intra- and postoperative complications remains uncertain. Small prospective or retrospective studies shown an decrease of the incidence of intraoperative adverse events and postoperative complications after a deep NMB. There is a need to confirm these outcome data prospectively, in a large number of patients and clinics and during a variety of surgical procedures.

Objective: To study the effect of deep neuromuscular block as compared to standard neuromuscular block on intra-operative adverse events during laparoscopic surgery.

Study design: Multi center, randomized controlled clinical trial

Study population: 922 patients planned for elective laparoscopic abdominal surgery.

Intervention: Patients will be randomized between a deep NMB (group 1; aimed at PTC 1-2) and standard care (group 2; standard care NMB).

Main study parameters/endpoints: Primary endpoint is the difference in incidence of intra-operative adverse events during laparoscopic surgery graded on the CLASSIC scale (*ie.* CLASSIC grade ≥ 2) between both groups

Secondary endpoints include the surgical working conditions, 30 day post-operative complications and quality of recovery.

Nature and extent of the burden and risks associated with participation, benefit and group

relatedness: The aim of this study is to compare two targets of neuromuscular block that are currently interchangeably used (both deep and standard NMB are routine practice at the LUMC).

Additionally, all other anesthesia and surgery related procedures (*eg.* medication and monitoring) follow routine practice. We therefore anticipate no additional risks from study related procedures.

Before surgery a Quality of Recovery and Short Form Health Survey will be obtained. After surgery the QoR-40 will be repeated twice, and the SF-36 will be obtained at 30 days after surgery.

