3. STUDY DESIGN

The EURO Relax is a multi-center, randomized controlled trial in patients undergoing laparoscopic abdominal surgery. Patients undergoing elective laparoscopic surgery in different fields of abdominal surgery will be randomized 1:1 in blocks of 2 and 4 to the deep or standard neuromuscular block group. Randomization will be stratified per center and BUPA category (MAJOR, MAJOR PLUS or COMPLEX MAJOR; for examples see table 1).

Patient inclusion will occur competitively in each center. Due to differences in inclusion rate, final inclusion could differ slightly in comparison with the proposed inclusion number per center.

[figure not shown]

Figure 1. Inclusion flowchart EURO Relax study. QoR: *quality of recovery*; *iAE*: *intraoperative adverse event*; L-SRS: *Leiden Surgical Rating Scale*; CCI: *composite complication index*.

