4.4 Sample size calculation

Preliminary data of the CLASSIC validation study as confidentially provided by dr. [name] (principle investigator; NCT03009929) confirm that the incidence of GRADE ≥ 2 iAEs (Table 2) is 20% for BUPA categories (unpublished data).

Table 2. Adapted version of the CLASSIC classification for intra-operative adverse events (*with permission of dr. [name] (principle investigator of the CLASSIC validation study; NCT03009929).*

Grade 0	No deviation from the ideal intraoperative course
Grade 1	Any deviation from the ideal intraoperative course without the need for any additional treatment or intervention; patient asymptomatic or mild symptoms
Grade 2	Any deviation from the ideal intraoperative course with the need for any additional minor treatment or intervention; patient with moderate symptoms, not life-threatening and not leading to permanent disability
Grade 3	Any deviation from the ideal intraoperative course with the need for any additional moderate treatment or intervention; patient with severe symptoms, potentially life-threatening and/or potentially leading to permanent disability
Grade 4	Any deviation from the ideal intraoperative course with the need for any additional major treatment or intervention; patient with life-threatening symptoms and/or leading to permanent disability
Grade 5	Any deviation from the ideal intraoperative course with intraoperative death of the patient

The following events are not defined as intraoperative complications: sequelae, failures of cure, events related to the underlying disease, wrong-site or wrong-patient surgery or errors in indication

- To date, the minimal clinically important difference (MCID) for intra-operative adverse events according to the CLASSIC classification has not been published. We consider a relative reduction in intra-operative adverse events, CLASSIC grade ≥ 2 , of 40% a clinically relevant difference. As de-

scribed above the reported average rate of grade 2 intra-operative Adverse Events (iAEs) is 20%.

- With an alpha of 5% and beta of 90%, 439 patients are required in each arm of the study (in total 878 patients).
 - Assuming a 5% rate of drop-out a total of 922 patients should be randomized 1:1 in this study. Reasons for drop-out are:
 - conversion to open surgery within the first 20 minutes of the procedure due to unforeseen adhesions, tumor progression, (peritoneal) metastases or other diagnosis

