8.2 Randomization, blinding and treatment allocation

Patient will be randomized between group 1 (deep NMB) or group 2 (standard care) just prior to surgery by an independent research nurse. Randomization will be performed using a dedicated, password protected website. The randomization sequence is generated by a dedicated computer randomization software; Castor (Castor EDC, CIWIT B.V., www.castoredc.com), stratified per center and BUPA category (MAJOR, MAJOR PLUS or COMPLEX MAJOR). To ensure a balanced distribution block, randomization will be used with 2 and 4 cases per block.

Blinding:

During every procedure, an unblinded researcher will be present to ensure adherence to the study protocol. Specifically, he or she will be responsible for maintaining the desired level of NMB. The researcher will not be involved in scoring of the Classic events (primary outcome). Classic scorings will be done by the attending anesthesiologist and surgeon who will be blinded.

To avoid deblinding of the surgical team in the standard NMB group (by noting the absence of a rocuronium perfusion), a syringe pump with NaCl 0.9% will substitute the rocuronium infusion.

Postoperative care nurses and the investigator assessing postoperative endpoints are blinded to group allocation. Additionally, data analysis will be performed by blinded researchers.

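### The primary chi-square test ignores the centre and BUPA strata used in the randomisation, giving up a small and nearly free gain in precision if those strata predict events

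*Combined protocol and SAP*

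**What the plan says.** Section 3 says "Randomization will be stratified per center and BUPA category", with patients allocated 1:1 in permuted blocks of 2 and 4. Section 8.2 repeats that the sequence is "stratified per center and BUPA category (MAJOR, MAJOR PLUS or COMPLEX MAJOR".

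For the primary endpoint, Section 10.1 reads "Data will be analyzed comparing the incidence of adverse events during laparoscopic surgery, following the Classic criteria using" a χ² test, significant at p < 0.05. Sections 10.2 to 10.4 do not use the strata for this endpoint. The linear mixed models in Section 10.2 are for longitudinal measurements such as heart rate, blood pressure and L-SRS.

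Section 4.4 gives one event rate, which "is 20% for BUPA categories (unpublished data", and nothing by category or centre. It concludes that "439 patients are required in each arm of the study (in total 878 patients".

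The Summary states that "Primary endpoint is the difference in incidence of intra-operative adverse events during laparoscopic surgery graded on the CLASSIC scale" between the groups. Section 10.1 names neither an estimate of that difference nor a confidence interval.

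**The concern.** Blocking within centre and BUPA category balances the arms within each stratum, so differences between strata largely cancel out of the treatment comparison. The plain chi-square test takes its variance from the pooled event rate and still counts those differences as noise. If the strata are prognostic, its standard error is too large: the test rejects less often than 5% under the null and loses some power under the alternative. If they are not prognostic, a stratified and an unstratified test nearly coincide.

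Prognostic strata are plausible, though the documents do not prove it. BUPA category is the protocol's own measure of case complexity, and Table 1 runs from cholecystectomy to hemi-hepatectomy and total cystectomy. Local surgeons and anaesthesiologists score the events, and Section 8.3 plans training and repeated checks so that centres score alike. At stake is precision that the stratified design has already paid for.

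**Working it through.** **1. The plan's own sample size.** Inputs from Section 4.4: control rate 20%; relative reduction 40%, so 12% in the deep-block arm; alpha 5%, taken as two-sided; the stated beta of 90% read as 90% power. The pooled formula for an unstratified comparison is

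n = [z₀.₉₇₅·√(2p̄(1−p̄)) + z₀.₉₀·√(p₀(1−p₀)+p₁(1−p₁))]² / (p₀−p₁)²

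with p̄ = 0.16:

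n = [1.960·√0.2688 + 1.282·√0.2656]² / 0.08² = (1.0162 + 0.6605)² / 0.0064 = 439.2 per arm.

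The plan says 439. Power of the plain test at 439 per arm is 90.0%, so the trial is sized for the test it names. The continuity-corrected version would need 464 per arm, so the plan's figure corresponds to the uncorrected test.

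**2. The tests compared.**
- Plain: Z = (p̂₀−p̂₁)/√[p̂(1−p̂)(1/N₀+1/N₁)].
- CMH over strata k: Z = Σ(e₀ₖ − n₀ₖmₖ/nₖ) / √Σ[n₀ₖn₁ₖmₖ(nₖ−mₖ)/(nₖ²(nₖ−1))], where e₀ₖ is events in one arm, n₀ₖ and n₁ₖ the arm sizes, mₖ total events and nₖ total patients in stratum k.

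Neither uses a continuity correction.

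**3. Type I error of the plain test.** If a share s of the outcome variance p(1−p) lies between strata, blocking shrinks the true variance by (1−s) and the test does not know it. Its type I error is about 2[1−Φ(1.96/√(1−s))]. For s = 5.7%: 1.96/√0.943 = 2.018, giving 4.4%.

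**4. Simulation.** 878 patients; overall rates calibrated to 20% and 12%; common odds ratio; permuted blocks of 2 and 4 within centre by BUPA; 40,000 null and 40,000 alternative trials per scenario. Assumptions, not document figures: 8 centres, BUPA shares 20/60/20%, and the stratum effects shown.

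| Assumed control rates by BUPA; centre SD (logit) | s | Type I, χ² | Power, χ² | Power, CMH | Gain (points) | Stratified 95% CI half-width (points) |
|---|---|---|---|---|---|---|
| Not prognostic | 0% | about 5% | 90.2% | 90.1% | −0.1 | 4.82 |
| 10/20/30%; none | 2.5% | 4.7% | 90.4% | 90.7% | 0.3 | 4.77 |
| 10/20/30%; 0.5 | 5.7% | 4.4% | 90.8% | 91.6% | 0.8 | 4.70 |
| 5/20/35%; 0.8 | 12.8% | 3.6% | 91.4% | 93.1% | 1.7 | 4.55 |

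The unstratified half-width for the risk difference is 4.81 points. CMH type I error is 4.8 to 4.9% in the prognostic cases. With equal BUPA shares, the widest case gives s = 16.2%, type I error 3.2%, and power 92.0% versus 94.0%.

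**5. A second set of assumptions** (8 centres, shares 30/45/25%, 10,000 trials per scenario). Power, plain versus CMH:
- not prognostic: 90.3% and 90.3%;
- mild (about 14/20/27%): 90.5% and 90.9%;
- moderate (11/19/32%): 91.1% and 92.1%;
- strong (9/19/35%): 90.9% and 92.9%;
- extreme (8/19/37%): 92.2% and 94.6%.

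In the moderate case s = 0.063, and 878/(1−0.063) is about 937 effective patients, 7% more than 878. With 4 or 15 centres the moderate gain is still about 1 point.

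**6. Sparse strata.** Section 3 says "Patient inclusion will occur competitively in each center", so uneven centres are plausible. With 20 uneven centres (assumed), 20% of strata hold fewer than 4 patients and CMH keeps 99.0% of the information; if the strata are not prognostic it loses 0.1 to 0.3 power points. Merging centres with fewer than 20 patients keeps 99.5%. Power, CMH versus plain, is then 90.0% versus 90.1% if the strata are not prognostic, and 91.3% versus 90.8% with 10/20/30% and centre SD 0.5.

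**The case against.** Nothing is lost against the plan. The 439 per arm was sized for the plain test, whose power is at least 90% in every scenario and rises when strata are prognostic. The shortfall exists only against a better alternative. No input behind the gain comes from the documents, and gains near 2 points need wide spreads, such as a sevenfold range in event rates across BUPA categories together with large centre differences. With weak prognosis (15/20/25%, no centre effect) CMH gains only 0.05 points with 8 centres and loses 0.14 points with 20 uneven, unmerged centres. CMH is also not the only method that would use the strata; covariate-adjusted logistic regression with standardisation would as well.

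Most of this stands as a limit on weight: the gain is conditional and likely to be 0 to 1 point, and the test as planned is valid. It does not remove the point. The weak-prognosis loss lies within the 0.1 to 0.3 points already shown for many uneven centres, and a pooling rule reduces it. The choice of CMH over adjusted regression is partly preference; what matters is fixing one stratified analysis in advance.

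The missing estimate and interval, and the silence on a continuity correction, are separate gaps that do not depend on the strata. A correction would cost either test about 1.3 to 1.9 power points, more than stratifying gains in the milder cases.

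**Conclusion.** The concern holds as an efficiency point. The design stratifies by centre and BUPA category and the primary test uses neither. Type I error is controlled and the planned 90% power is met, so this is an improvement that should be made, not a defect that invalidates the analysis.

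Stratifying is worth roughly 0 to 1 power point with no to moderate stratum effects and about 1.7 to 2.5 points with wide ones. The confidence interval narrows from a half-width of 4.81 points to between 4.77 and 4.55 in the prognostic cases with 20/60/20% shares. The downside is 0.1 to 0.3 power points with many uneven centres and strata that predict little. These sizes rest on assumed numbers of centres, BUPA shares and stratum rates. The absence of an effect estimate and interval rests on no assumption.

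**What to change.** Amend Section 10.1 before unblinding; a stratified analysis chosen later would look data-driven.

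- **Primary test:** one two-sided Cochran-Mantel-Haenszel test of CLASSIC grade 2 or higher events, stratified by centre and by BUPA category as recorded at randomisation, without continuity correction, at the 5% level.
- **Small centres:** for example, all centres with fewer than 20 randomised patients in total, counted over all BUPA categories, are merged into one centre, and the BUPA strata are kept within it. Fix the grouping before unblinding.
- **Estimate:** the Mantel-Haenszel risk difference and risk ratio, each with a 95% confidence interval.
- **Sensitivity analysis:** the plain chi-square test, also without continuity correction.

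The cost is two or three sentences. No new data or patients are needed, since both factors are already in the randomisation system.

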10.2 Secondary study parameters

Continuous normally distributed variables will be expressed by their mean and standard deviation or when not normally distributed as medians and their interquartile ranges. Categorical variables will be expressed as n (%). To test groups Student's t test will be used, if continuous data are not normally distributed the Mann-Whitney U test will be used. Categorical variables will be compared with the Chi-square test or Fisher's exact tests. P-values < 0.05 will be considered significant for the primary outcome. A cut off p-value of < 0.01 will be applied for secondary outcomes.

Data analysis will be performed using R Studio, Boston, MA, USA..

Longitudinal data (heart rate, blood pressure, L-SRS, BIS levels compared to the depth of NMB at the given moment) will be analyzed using linear mixed models. NONMEM (ICON Development Solutions, Ellicott, MD, USA), will be used for statistical analysis.

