8.1.1 Secondary study parameters/endpoints

To study the effect of deep neuromuscular block as compared to standard neuromuscular block on:

- Surgical working conditions (L-SRS, Table 3)
- 30-day post-operative complications (Clavien-Dindo, Table 6)
- 30-day post-operative complications according to the Comprehensive Complication Index
- 30-day unplanned readmission rates
- Quality of recovery at post-operative day 1, 2 and 30 after laparoscopic surgery.
 - Quality-of-recovery (QoR-40 at postoperative day 1 and 2; Aldrete score (Table 5) at the PACU)
 - Quality-of-life at postoperative day 30 (SF36, Appendix 2)

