8.1.2 Other study parameters

- Patient age, gender, length and weight, ASA class, underlying disease(s), planned procedure, blood pressure and heart rate, center of admission
- Pre-operative NRS, QoR-40 and SF 36
- Per operative the following variables will be noted, after installation of the pneumoperitoneum at 15 minute intervals until the end of the surgery. At these moments the L-SRS is also scored:
 - Heart rate (/min), blood pressure in mmHg
 - Intra-abdominal pressure in mmHg and total insufflations volume (in Liters)
 - Depth of anesthesia: Bispectral Index and end-tidal sevoflurane
 - Depth of NMB (TOF count and/or PTC)
 - Duration of surgery and anesthesia
 - Time of extubation
 - Cumulative drug dosages (propofol, opioids, muscle relaxant, reversal agent, inotropics, NSAIDS's or metamizol)
 - Core temperature in degrees Celsius
 - Surgical satisfaction with the anesthesia: 'very dissatisfied', 'dissatisfied', 'satisfied' tot 'very satisfied'.
- Postoperative recovery scores:
 - Time to discharge readiness (Aldrete score ≥ 9 and NRS < 5)
 - Heart rate (/min), blood pressure in mmHg
 - peripheral oxygen saturation, respiratory rate (/min), use of supplemental O₂ (in liters/minute)
 - NRS and administration of analgesic medication
 - Ramsay sedation scale and Aldrete score
 - Nausea or vomiting

- Length of admission at the PACU and/or ICU (if applicable) and duration of hospital admission
 - Pain scores (numeric rating scale; NRS 0 no pain – 10 worst pain imaginable) at movement (and rest) three times daily until discharge or to a maximum of 72 hours will be extracted from the patient clinical charts.
 - Medication use (three times daily until discharge or to a maximum of 72 hours) will be extracted from the patient clinical charts.
 - Cumulative opiate use
 - Cumulative use of other analgesics and anti-emetics

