8.3 Study procedures

Informed consent procedure

Patients will be screened for eligibility on the routine preoperative visit at the anesthesia outpatient department. Should a patient be eligible, than he or she will be contacted by one of the researchers by phone to receive oral and written information about the study. This contact will take place at least 2 weeks prior to the surgical procedure. If the patient is willing to participate, written consent will be obtained

Preoperative procedures

After informed consent has been obtained, baseline QoR-40 and SF36 questionnaires will be taken prior to surgery and randomization.

Perioperative procedures

Anesthesia procedures: Anesthesia procedures will follow local protocol on all aspects, except for

the neuromuscular block. Standard anesthesia iv access and standard monitoring according to local institutional protocol will be applied. General anesthesia will be induced and maintained with propofol or sevoflurane or desflurane. Intraoperative antinociceptive treatment will be with sufentanil, fentanyl or remifentanil. The choice regarding the type of hypnotic and opioid is upon the discretion of the attending anesthesiologist and is not influenced by this study. Hypnotic depth of all patients will be routinely monitored with bispectral index monitoring (BIS module, Philips, Eindhoven, The Netherlands) or entropy assessment to assess the level of hypnosis. The target level of the BIS is 50 +/- 5 during the procedure, and propofol dosage or end-tidal sevoflurane/desflurane will be steered to maintain the target BIS level to avoid under- or overdosing of the hypnotic agent.

Postoperative pain relief will be ensured with morphine, or equivalent (eg. Piritramide or methadone), and NSAIDs (eg. Diclofenac 50 - 75 mg) or metamizole 1g, and acetaminophen 1g. Lidocaine iv, magnesium, β -blocking agents, and/or loco-regional infiltration / techniques are not allowed.

Ventilation: will be adjusted to maintain end-tidal pCO₂ of 4.5 to 5.5 kPa.

Postoperative pain relief. Pain relief at the PACU is left to at discretion of the attending anesthesiologists. All analgesics that are administered will be recorded in the e-CRF

Neuromuscular management

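### QoR-40 and SF-36 are measured before randomisation, but section 10.2 compares the follow-up scores without baseline adjustment, losing precision on secondary endpoints judged at p < 0.01

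*Combined protocol and SAP*

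**What the plan says.** - **Baseline.** Section 8.3 (Preoperative procedures) states that "baseline QoR-40 and SF36 questionnaires will be taken prior to surgery and randomization". Section 8.1.2 lists the same scores among the recorded variables: "Pre-operative NRS, QoR-40 and SF 36".
- **Endpoints.** Section 8.1.1 has a secondary endpoint group headed "Quality of recovery at post-operative day 1, 2 and 30 after laparoscopic surgery". It contains QoR-40 on days 1 and 2 and SF-36 on day 30. Section 2 makes better early quality of recovery part of the secondary hypotheses.
- **Analysis.** For continuous secondary outcomes section 10.2 gives Student's t test, and "if continuous data are not normally distributed the Mann-Whitney U test will be used". The threshold is stricter than for the primary outcome: "A cut off p-value of < 0.01 will be applied for secondary outcomes".
- **What is absent.** Section 10.2 names no baseline covariate, ANCOVA or change score. Its linear mixed models are for heart rate, blood pressure, L-SRS and BIS. Section 10.3 says pre-operative pain scores will be reported but does not mention baseline QoR-40 or SF-36. Sections 3 and 8.2 stratify randomisation by centre and BUPA category, and neither factor enters the tests in 10.2.

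**The concern.** A patient's score after surgery is likely to depend partly on the score before it. A two-sample test leaves that between-patient variation in the error term, so the interval for the treatment difference is wider than it needs to be. A chance difference between the arms at baseline also passes, in proportion to r, into the estimated effect.

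This counts for more here because the 0.01 threshold already raises the difference that the trial can reliably detect. A true improvement in recovery could be missed although the data that would sharpen the comparison are in the database.

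The normality rule adds a second weakness. It lets the data choose both the test and the summary reported (mean or median), and the rank test gives no adjusted mean difference. With about 440 patients per arm, a linear model for a mean difference does not need such a gate.

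**Working it through.** **Inputs from the documents.** 439 evaluable patients per arm (section 4.4) and alpha 0.01 for secondary outcomes (section 10.2; sidedness is not stated, two-sided assumed).

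**Assumptions, not in the documents.** The correlation r between baseline and follow-up, and an illustrative true difference of 0.2 SD.

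**The plan's own figure.** The plan gives no power for QoR-40 or SF-36. The 439 comes from the primary endpoint: 20% against 12%, alpha 5%, power 90%. The pooled formula gives

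[1.960 × √(2 × 0.16 × 0.84) + 1.282 × √(0.20 × 0.80 + 0.12 × 0.88)]² / 0.08² = 439.2,

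which agrees with the plan.

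**Step 1: precision.** ANCOVA on the baseline score multiplies the residual variance by 1 − r². Interval width is multiplied by √(1 − r²). The equivalent number of patients per arm in an unadjusted analysis is 439 / (1 − r²).

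**Step 2: power for 0.2 SD.** The non-centrality without adjustment is 0.2 × √(439/2) = 2.963. Power = Φ(2.963 / √(1 − r²) − 2.576).

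**Step 3: difference detectable with 80% power.** (2.576 + 0.842) × √(2/439) × √(1 − r²).

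| r (assumed) | Variance factor | Equivalent n per arm | Power for 0.2 SD | Detectable difference, 80% power |
|---|---|---|---|---|
| 0 (plan) | 1.00 | 439 | 65% | 0.231 SD |
| 0.3 | 0.91 | 482 (+10%) | 70% | 0.220 SD |
| 0.5 | 0.75 | 585 (+33%) | 80% | 0.200 SD |
| 0.6 | 0.64 | 686 (+56%) | 87% | 0.185 SD |

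**Step 4: against the cost of the 0.01 threshold.** At alpha 0.05 the unadjusted detectable difference would be (1.960 + 0.842) × √(2/439) = 0.189 SD. The stricter threshold raises it to 0.231 SD. Adjustment recovers all of that when √(1 − r²) = 2.802/3.418 = 0.820, that is, at r of about 0.57. At lower r it recovers part.

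**Step 5: simulation.** Normal data, 439 per arm, alpha 0.01, 3,000 trials per setting. With no true difference, the t test, Mann-Whitney and ANCOVA each rejected in about 1% of trials. With a true difference of 0.23 SD, the t test had 79–81% power and Mann-Whitney 77–78%. ANCOVA had 84.8%, 90.7% and 98.5% at r = 0.3, 0.5 and 0.7.

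**Step 6: if a change score is meant.** With equal variances at the two times, a change score has variance 2(1 − r) relative to the raw score. That is worse than ignoring baseline when r < 0.5. It is never better than ANCOVA, because 2(1 − r) − (1 − r²) = (1 − r)² ≥ 0.

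**The case against.** The strongest reply is that nothing in the plan is wrong. Under 1:1 randomisation the unadjusted tests are unbiased and hold their error rate, and the plan claims no power for these endpoints. That stands, and it is why the point is a recommendation and not a defect in validity.

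Several narrower points also stand:

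- **Size.** Neither r nor the 0.2 SD is in the documents. At r = 0.3 the gain is about 5 points of power. QoR-40 on days 1 and 2 reflects acute recovery and may correlate less with baseline than SF-36 on day 30.
- **Numbers available.** The drop-out reasons in section 4.4 make no allowance for questionnaires that are not returned, so the absolute power figures are optimistic. The relative gain, 1 / (1 − r²), does not depend on n.
- **Chance imbalance.** The standard error of a baseline difference is √(2/439) = 0.068 SD, and the unadjusted test already allows for this in its error rate. It is the same loss of precision seen from another side, not a second harm.
- **Rank test.** Mann-Whitney is legitimate for skewed or bounded scores, and it cost only a few points of power in the simulation.
- **Wording.** Section 10.2 is generic and does not mention either questionnaire, so a change score cannot be strictly ruled out. No text supports one, and it would not outperform ANCOVA.

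None of this reverses the direction. Any non-zero r gives a gain, and if r is near zero one extra covariate costs almost nothing with 878 patients.

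**Conclusion.** The concern holds. Section 10.2 gives no role to baseline scores that every patient is asked to provide, on endpoints tied to a stated secondary hypothesis and judged at 0.01. The consequence is wider intervals and lower power, not bias. The primary analysis and the sample size are not touched.

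Over an assumed r of 0.3 to 0.6, the plan gives up precision worth 10% to 56% more patients. For an assumed 0.2 SD difference with 439 complete cases per arm, that is 5 to 22 points of power (70 − 65 and 87 − 65). The gain may be near the lower end for early QoR-40. The absence of adjustment is certain from the text; its size is not, because it rests on r. The change should be made.

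**What to change.** Amend section 10.2 before unblinding, so that the adjustment cannot appear to have been chosen by its result:

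1. **QoR-40.** Analyse days 1 and 2 in one linear mixed model with arm, day, arm by day, baseline QoR-40, BUPA category and centre. State which contrast (day 1, day 2 or both) is held to the 0.01 threshold.
2. **SF-36.** Analyse day 30 by ANCOVA with the matching baseline score, BUPA category and centre. Name the SF-36 score or scores to be analysed, since the plan names none. BUPA category and centre belong in both models because randomisation is stratified on them.
3. **Reporting.** Give adjusted mean differences with confidence intervals. Drop the normality rule for these endpoints and keep the unadjusted or rank tests as sensitivity analyses.
4. **Missing baseline.** State a simple rule, for example mean imputation of the baseline covariate.

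The cost is SAP wording and the choice of SF-36 score. The data are already planned, section 10.2 already uses mixed models for other outcomes, and no patient procedure or sample size changes.
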